14.3.7 Displays of 12-Lead Standard Measurements

Table 27: 12-Lead Standard ECG Overall Interpretations, Post Dose Compared to Baseline

Change from Baseline in ECG Interpretation	2 g Zoliflodacin n (%)	4 g Zoliflodacin n (%)	Placebo n (%)	400 mg Moxifloxacin n (%)	Any Period n (%)
1 h Post-dose					
	N=X	N=X	N=X	N=X	N=X
Normal at Both Times	x (x)	x (x)	x (x)	x (x)	x (x)
Normal to Abnormal, NCS	x (x)	x (x)	x (x)	x (x)	x (x)
Normal to Abnormal, CS	x (x)	x (x)	x (x)	x (x)	x (x)
Abnormal, NCS at Both Times	x (x)	x (x)	x (x)	x (x)	x (x)
Abnormal, NCS to Abnormal, CS	x (x)	x (x)	x (x)	x (x)	x (x)
Abnormal, NCS to Normal	x (x)	x (x)	x (x)	x (x)	x (x)
2 h Post-dose					
	N=X	N=X	N=X	N=X	N=X
Normal at Both Times	x (x)	x (x)	x (x)	x (x)	x (x)
Normal to Abnormal, NCS	x (x)	x (x)	x (x)	x (x)	x (x)
Normal to Abnormal, CS	x (x)	x (x)	x (x)	x (x)	x (x)
Abnormal, NCS at Both Times	x (x)	x (x)	x (x)	x (x)	x (x)
Abnormal, NCS to Abnormal, CS	x (x)	x (x)	x (x)	x (x)	x (x)
Abnormal, NCS to Normal	x (x)	x (x)	x (x)	x (x)	x (x)
4 h Post-dose					
	N=X	N=X	N=X	N=X	N=X
Normal at Both Times	x (x)	x (x)	x (x)	x (x)	x (x)
Normal to Abnormal, NCS	x (x)	x (x)	x (x)	x (x)	x (x)
Normal to Abnormal, CS	x (x)	x (x)	x (x)	x (x)	x (x)
Abnormal, NCS at Both Times	x (x)	x (x)	x (x)	x (x)	x (x)
Abnormal, NCS to Abnormal, CS	x (x)	x (x)	x (x)	x (x)	x (x)
Abnormal, NCS to Normal	x (x)	x (x)	x (x)	x (x)	x (x)
24 h Post-dose					
	N=X	N=X	N=X	N=X	N=X
Normal at Both Times	x (x)	x (x)	x (x)	x (x)	x (x)
Normal to Abnormal, NCS	x (x)	x (x)	x (x)	x (x)	x (x)
Normal to Abnormal, CS	x (x)	x (x)	x (x)	x (x)	x (x)
Abnormal, NCS at Both Times	x (x)	x (x)	x (x)	x (x)	x (x)
Abnormal, NCS to Abnormal, CS	x (x)	x (x)	x (x)	x (x)	x (x)
Abnormal, NCS to Normal	x (x)	x (x)	x (x)	x (x)	x (x)

Change from Baseline in ECG Interpretation	2 g Zoliflodacin n (%)	4 g Zoliflodacin n (%)	Placebo n (%)	400 mg Moxifloxacin n (%)	Any Period n (%)
Follow-up^a					
	N=X	N=X	N=X	N=X	N=X
Normal at Both Times	x (x)	x (x)	x (x)	x (x)	x (x)
Normal to Abnormal, NCS	x (x)	x (x)	x (x)	x (x)	x (x)
Normal to Abnormal, CS	x (x)	x (x)	x (x)	x (x)	x (x)
Abnormal, NCS at Both Times	x (x)	x (x)	x (x)	x (x)	x (x)
Abnormal, NCS to Abnormal, CS	x (x)	x (x)	x (x)	x (x)	x (x)
Abnormal, NCS to Normal	x (x)	x (x)	x (x)	x (x)	x (x)
Pre-dose (Prior to Next Dose)					
	N=X	N=X	N=X	N=X	N=X
Normal at Both Times	x (x)	x (x)	x (x)	x (x)	x (x)
Normal to Abnormal, NCS	x (x)	x (x)	x (x)	x (x)	x (x)
Normal to Abnormal, CS	x (x)	x (x)	x (x)	x (x)	x (x)
Abnormal, NCS at Both Times	x (x)	x (x)	x (x)	x (x)	x (x)
Abnormal, NCS to Abnormal, CS	x (x)	x (x)	x (x)	x (x)	x (x)
Abnormal, NCS to Normal	x (x)	x (x)	x (x)	x (x)	x (x)
Final Visit^b					
	N=X	N=X	N=X	N=X	N=X
Normal at Both Times	x (x)	x (x)	x (x)	x (x)	x (x)
Normal to Abnormal, NCS	x (x)	x (x)	x (x)	x (x)	x (x)
Normal to Abnormal, CS	x (x)	x (x)	x (x)	x (x)	x (x)
Abnormal, NCS at Both Times	x (x)	x (x)	x (x)	x (x)	x (x)
Abnormal, NCS to Abnormal, CS	x (x)	x (x)	x (x)	x (x)	x (x)
Abnormal, NCS to Normal	x (x)	x (x)	x (x)	x (x)	x (x)

Note: N = number of subjects in safety population with the ECG measurement at the respective time point.

CS = clinically significant; NCS = not clinically significant.

^a The “Follow-up” analysis time points refer to either Check-In visits for the next period (for analysis of treatments given in Period 1, 2, or 3) or to the Final Visit with Pre-dose 4 as baseline.

^b The “Final Visit” analysis time point uses the last measurement prior to the first dose as baseline.

Table 28: 12-Lead Standard ECG Results by Parameter, Maximum Severity, Time Point, and Dosing Period

[Implementation Note: If there is not at least 1 Mild, Moderate, or Severe Event for Any Period, Max Severity Post-Baseline, then only the Any Period, Max Severity Post-Baseline row will be shown for the parameter.]

Dosing Period	Time Point	N	Mild		Moderate		Severe	
			n	%	n	%	n	%
PR Interval Prolongation								
Any Period	Max Severity Post-Baseline	x	x	x	x	x	x	x
	1 h Post-dose	x	x	x	x	x	x	x
	2 h Post-dose	x	x	x	x	x	x	x
	4 h Post-dose	x	x	x	x	x	x	x
	24 h Post-dose	x	x	x	x	x	x	x
	Follow-up ^a	x	x	x	x	x	x	x
	Pre-dose (Prior to Next Dose)	x	x	x	x	x	x	x
	Final Visit ^b	x	x	x	x	x	x	x
2 g Zoliflodacin	Max Severity Post-Baseline	x	x	x	x	x	x	x
	1 h Post-dose	x	x	x	x	x	x	x
	2 h Post-dose	x	x	x	x	x	x	x
	4 h Post-dose	x	x	x	x	x	x	x
	24 h Post-dose	x	x	x	x	x	x	x
	Follow-up ^a	x	x	x	x	x	x	x
	Pre-dose (Prior to Next Dose)	x	x	x	x	x	x	x
4 g Zoliflodacin	Max Severity Post-Baseline	x	x	x	x	x	x	x
	1 h Post-dose	x	x	x	x	x	x	x
	2 h Post-dose	x	x	x	x	x	x	x
	4 h Post-dose	x	x	x	x	x	x	x
	24 h Post-dose	x	x	x	x	x	x	x
	Follow-up ^a	x	x	x	x	x	x	x
	Pre-dose (Prior to Next Dose)	x	x	x	x	x	x	x
Placebo	Max Severity Post-Baseline	x	x	x	x	x	x	x
	1 h Post-dose	x	x	x	x	x	x	x
	2 h Post-dose	x	x	x	x	x	x	x
	4 h Post-dose	x	x	x	x	x	x	x
	24 h Post-dose	x	x	x	x	x	x	x
	Follow-up ^a	x	x	x	x	x	x	x
	Pre-dose (Prior to Next Dose)	x	x	x	x	x	x	x
400 mg Moxifloxacin	Max Severity Post-Baseline	x	x	x	x	x	x	x
	1 h Post-dose	x	x	x	x	x	x	x

Dosing Period	Time Point	N	Mild		Moderate		Severe	
			n	%	n	%	n	%
	2 h Post-dose	x	x	x	x	x	x	x
	4 h Post-dose	x	x	x	x	x	x	x
	24 h Post-dose	x	x	x	x	x	x	x
	Follow-up ^a	x	x	x	x	x	x	x
	Pre-dose (Prior to Next Dose)	x	x	x	x	x	x	x
QTcF Prolongation								
Any Period	Max Severity Post-Baseline	x	x	x	x	x	x	x
	1 h Post-dose	x	x	x	x	x	x	x
	2 h Post-dose	x	x	x	x	x	x	x
	4 h Post-dose	x	x	x	x	x	x	x
	24 h Post-dose	x	x	x	x	x	x	x
	Follow-up ^a	x	x	x	x	x	x	x
	Pre-dose (Prior to Next Dose)	x	x	x	x	x	x	x
	Final Visit ^b	x	x	x	x	x	x	x
2 g Zoliflodacin	Max Severity Post-Baseline	x	x	x	x	x	x	x
	1 h Post-dose	x	x	x	x	x	x	x
	2 h Post-dose	x	x	x	x	x	x	x
	4 h Post-dose	x	x	x	x	x	x	x
	24 h Post-dose	x	x	x	x	x	x	x
	Follow-up ^a	x	x	x	x	x	x	x
	Pre-dose (Prior to Next Dose)	x	x	x	x	x	x	x
4 g Zoliflodacin	Max Severity Post-Baseline	x	x	x	x	x	x	x
	1 h Post-dose	x	x	x	x	x	x	x
	2 h Post-dose	x	x	x	x	x	x	x
	4 h Post-dose	x	x	x	x	x	x	x
	24 h Post-dose	x	x	x	x	x	x	x
	Follow-up ^a	x	x	x	x	x	x	x
	Pre-dose (Prior to Next Dose)	x	x	x	x	x	x	x
Placebo	Max Severity Post-Baseline	x	x	x	x	x	x	x
	1 h Post-dose	x	x	x	x	x	x	x
	2 h Post-dose	x	x	x	x	x	x	x
	4 h Post-dose	x	x	x	x	x	x	x
	24 h Post-dose	x	x	x	x	x	x	x
	Follow-up ^a	x	x	x	x	x	x	x
	Pre-dose (Prior to Next Dose)	x	x	x	x	x	x	x

Dosing Period	Time Point	N	Mild		Moderate		Severe	
			n	%	n	%	n	%
400 mg Moxifloxacin	Max Severity Post-Baseline	x	x	x	x	x	x	x
	1 h Post-dose	x	x	x	x	x	x	x
	2 h Post-dose	x	x	x	x	x	x	x
	4 h Post-dose	x	x	x	x	x	x	x
	24 h Post-dose	x	x	x	x	x	x	x
	Follow-up ^a	x	x	x	x	x	x	x
	Pre-dose (Prior to Next Dose)	x	x	x	x	x	x	x

Note: The “Max Severity Post-Baseline” rows indicate the maximum severity experienced by each subject at any time point post baseline within the period, including unscheduled assessments. N = number of subjects in safety population with the ECG measurement at the respective time point.

^a The “Follow-up” analysis time points refer to either Check-In visits for the next period (for analysis of treatments given in Period 1, 2, or 3) or to the Final Visit with Pre-dose 4 as baseline.

^b The “Final Visit” analysis time point uses the last measurement prior to the first dose as baseline.

Table 29: 12-Lead Standard ECG Change from Baseline – Summary Statistics by Parameter, Time Point, and Dosing Period

[Implementation Note: The following 12-lead standard ECG parameters will be summarized, in order:]

Dosing Period	Time Point	N	Mean	SD	Median	Min, Max
PR Interval (msec)						
2 g Zoliflodacin	1 h Post-dose	x	x	x	x	x
	2 h Post-dose	x	x	x	x	x
	4 h Post-dose	x	x	x	x	x
	24 h Post-dose	x	x	x	x	x
	Follow-up ^a	x	x	x	x	x
	Pre-dose (Prior to Next Dose)	x	x	x	x	x
4 g Zoliflodacin	1 h Post-dose	x	x	x	x	x
	2 h Post-dose	x	x	x	x	x
	4 h Post-dose	x	x	x	x	x
	24 h Post-dose	x	x	x	x	x
	Follow-up ^a	x	x	x	x	x
	Pre-dose (Prior to Next Dose)	x	x	x	x	x
Placebo	1 h Post-dose	x	x	x	x	x
	2 h Post-dose	x	x	x	x	x
	4 h Post-dose	x	x	x	x	x
	24 h Post-dose	x	x	x	x	x
	Follow-up ^a	x	x	x	x	x
	Pre-dose (Prior to Next Dose)	x	x	x	x	x
400 mg Moxifloxacin	1 h Post-dose	x	x	x	x	x
	2 h Post-dose	x	x	x	x	x
	4 h Post-dose	x	x	x	x	x
	24 h Post-dose	x	x	x	x	x
	Follow-up ^a	x	x	x	x	x
	Pre-dose (Prior to Next Dose)	x	x	x	x	x
Dosing Period 4	Final Visit ^b	x	x	x	x	x
QRS Duration (msec)						
...						

Note: N= number of subjects in safety population with the ECG measurement at the respective time point.

^a The “Follow-up” analysis time points refer to either Check-In visits for the next period (for analysis of treatments given in Period 1, 2, or 3) or to the Final Visit with Pre-dose 4 as baseline.

^b The “Final Visit” analysis time point uses the last measurement prior to the first dose as baseline.

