- Measurements taken during the Final Visit will use the last measurement prior to the first dose as baseline for the analysis time points labeled “Final Visit” and will use the last measurement prior to the fourth dose as baseline for the analysis time points labeled “Follow-up”. Listings will show both of the two change from baseline values for Final Visit. The justification for including the Period 1 baseline for the Final Visit is to show overall changes (ideally absence of changes) over the course of the study. Grading of change from baseline will be based on the Period 1 baseline only.

Treatment Associated with Records

Treatment associated with post-dose records will always be the last type of treatment received before the (start) date or date-time associated with the record. AEs will be summarized by treatment and listings of all safety endpoints will include treatment, as it is defined here.

Possible values of treatment, in order of presentation in the CSR, are: 2 g zoliflodacin, 4 g zoliflodacin, placebo, and 400 mg moxifloxacin.

Study Day and Day in Period

Study Day and Day in Period will primarily be used in listings to refer to timing of assessments and events relative to first dosing (Study Day) or dose for the respective period (Day in Period).

The day that the first dose of study product is received is considered Study Day 1 for each subject. The day prior to first dose is considered Study Day = -1, not Study Day = 0.

The day that the dose of study product is received is considered Day in Period = 1 for each subject and each dosing period. The day prior to dosing for each period is considered Day in Period = -1, not Day in Period = 0.

Treatment Sequence

Each subject will receive one dose orally of each of four treatments, labeled A through D:

- Treatment A: zoliflodacin 2 g
- Treatment B: zoliflodacin 4 g
- Treatment C: placebo
- Treatment D: moxifloxacin 400 mg

Each subject will be randomly allocated to one of 12 dosing sequences before dosing on Day 1, Dosing Period 1, and receive a single dose of the preceding four study drugs on different days according to their randomly-assigned dosing sequences. The 12 dosing sequences, in order that they will be presented in the report, are ABCD, ACDB, ADBC, BADC, BDCA, BCAD, CDAB, CABD, CBDA, DCBA, DBAC, and DACB.

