9. SAFETY EVALUATION

All safety analyses will be presented using the safety population. Subjects will be grouped for summary statistics by Treatment, as defined in Section 3.3.

When calculating the incidence of AEs (i.e., on a per subject basis), each subject will be counted once and any repetitions of unsolicited AEs within a subject (by treatment) will be ignored for events coded in the same category by the Medical Dictionary for Regulatory Activities (MedDRA®). The denominators for percent values will be indicated within the table or table header and denominators will consist of the maximal size of the safety population in the indicated observation period. Moreover, events thus summarized will be coded to the highest severity observed. If the time interval defined by the start date and end date of the AE overlaps more than 1 period, the AE will be associated with treatment immediately preceding the AE start date only, and the AE will be graded according to the maximum severity of the event at any time prior to the AE end date. Abnormal laboratory values or clinical findings measured after dosing will be reported using the toxicity scales in [Table 3](#) and [Table 4](#).

All laboratory, vital signs, and ECG results obtained after the first dose that have programmable criteria described in the toxicity scales will be graded for the CSR according to the programmable criteria, and toxicity grades of mild, moderate, or severe will be indicated for the result in the listings. For criteria involving a change from baseline, the baseline to be used is described in Section 3.3.

If a subject was accepted into the trial with a laboratory, vital signs, or ECG parameter value that overlaps with values used for grading Grade 1 laboratory abnormalities, the result will only be graded (mild or worse) if the post-dose measurement of the parameter is different (worse) than baseline. In other words, a result will be graded as mild, moderate, or severe if and only if it both meets the grading criteria in [Table 3](#) or [Table 4](#) and is worse than baseline by any amount.

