- If the first replicate is abnormal, the second replicate is normal, and the third replicate is normal, then the second replicate will be used in the analysis.
- If the first replicate is abnormal, the second replicate is normal, and the third replicate is abnormal, then the first replicate will be used if has a severity equal to or greater to the third replicate, or the third replicate will be used if the third replicate has a higher severity than the first replicate.

Vital signs replicates not used in the analysis will not be listed.

PE findings will be listed ([Listing 16](#)).

9.8. 12-Lead Standard ECG

Toxicity grade criteria for 12-lead standard ECG parameters (PR and QTcF intervals) can be found in [Table 3](#). 12-lead standard ECG interval measurements ([Listing 17](#)), and overall interpretation and comments ([Listing 18](#)) will be listed. Unplanned 12-lead standard ECG measurements will be listed but excluded from tabular and graphical summaries.

12-lead standard ECG results will be summarized in tables and figures:

- Tabularly, 12-lead standard ECG change in overall interpretation from baseline will be shown by treatment and time point in [Table 27](#).
- Tabularly, by parameter, treatment, time point, and toxicity grade (including maximum severity post-baseline) ([Table 28](#))
- Tabularly, by summary statistics for change from baseline, reported by parameter, treatment, and time point ([Table 29](#))

-
- Graphically, using box plots showing the change from baseline by parameter, treatment, and time point ([Figure 44](#), [Figure 45](#), [Figure 46](#), [Figure 47](#), [Figure 48](#), [Figure 49](#))

The following parameters will be presented (in order): PR Interval; QRS Duration, QT Interval; QTcF Interval, RR Interval; ECG Mean Ventricular Rate.

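### SAP Table 27 sets out the Final Visit ECG shift from the pre-first-dose baseline by treatment, so a change spanning all four drugs is reported under the last one given

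*SAP*

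**What the plan says.** SAP 9.8 plans Table 27 so that the "change in overall interpretation from baseline will be shown by treatment and time point". The shell has five columns: the four treatments and Any Period. Its last block, Final Visit, has an N and count cells in all five, and a footnote states that this "analysis time point uses the last measurement prior to the first dose as baseline".

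SAP 3.3 gives the same baseline rule and explains why: using the Period 1 baseline at the Final Visit "is to show overall changes (ideally absence of changes) over the course of the study". The same ECG is also compared with the reading before dose 4. That comparison appears in the Follow-up block.

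Two rules decide which column a subject enters. SAP 3.3: "Treatment associated with post-dose records will always be the last type of treatment received before the (start) date or date-time associated with the record". SAP 9: "Subjects will be grouped for summary statistics by Treatment, as defined in Section 3.3". Table 27 has no implementation note that overrides either rule for the Final Visit block.

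**The concern.** The baseline and the column describe different things. The baseline reaches back to before the first dose, so the shift covers the whole crossover. The column names only the drug given in Period 4. A reader who sees a count of 'Normal to Abnormal' shifts under placebo will take it as change after placebo, when each completer in that column had both zoliflodacin doses and moxifloxacin after the baseline reading.

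At stake is how one part of the safety ECG table is read. Change in ECG parameters after zoliflodacin and moxifloxacin is a listed secondary outcome, and columns by drug invite comparison across drugs. In this block that comparison has no meaning.

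**Working it through.** **Inputs.** SAP 3.3 lists 12 sequences: ABCD, ACDB, ADBC, BADC, BDCA, BCAD, CDAB, CABD, CBDA, DCBA, DBAC, DACB (A = 2 g, B = 4 g, C = placebo, D = moxifloxacin). SAP 4.1 plans 6 subjects per sequence.

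**Plan's own figure.** 12 × 6 = 72, as stated.

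**Size of each Final Visit column.** Count the sequences by their last letter:

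| Last treatment | Sequences | Subjects if all complete |
|---|---|---|
| A, 2 g | BDCA, CBDA, DCBA | 3 × 6 = 18 |
| B, 4 g | ACDB, CDAB, DACB | 3 × 6 = 18 |
| C, placebo | ADBC, BADC, DBAC | 3 × 6 = 18 |
| D, moxifloxacin | ABCD, BCAD, CABD | 3 × 6 = 18 |

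These are ceilings. The sample-size section allows up to 16 withdrawals before replacement. With 72 − 16 = 56 completers spread evenly over the sequences (an assumption), each column would hold 56 / 4 = 14.

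**What a column contains.** Every completer has had all four treatments between the pre-first-dose reading and the Final Visit. The four columns therefore have the same cumulative exposure and differ only in which drug came last.

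**Worked case.** A subject in ADBC is normal before dose 1, becomes abnormal but not clinically significant (NCS) after one of the first three drugs, and is still so before dose 4 and at the Final Visit.

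- Final Visit block (baseline before dose 1): 'Normal to Abnormal, NCS', placebo column.
- Follow-up block (baseline before dose 4): 'Abnormal, NCS at Both Times', placebo column.

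The second entry correctly shows no new change after placebo. The first is a true statement about the whole study, but it sits under a heading that ties it to placebo.

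**Other safety shells with the same Final Visit time point.**

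| Tables | Where Final Visit is shown |
|---|---|
| 20, 25, 28 (22 and 24 repeat 20) | Any Period only |
| 21, 26, 29 (23 repeats 21) | One row labelled Dosing Period 4 |
| 27 | All four treatment columns and Any Period |

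Table 27 is the only one that splits the Final Visit by drug. This looks like a layout carried over from the blocks above it.

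**The case against.** Several points on the other side are sound.

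- **Nothing is displaced.** A reader might infer that abnormalities are taken away from the drug that preceded them. They are not. An abnormality seen after zoliflodacin is counted under zoliflodacin, against that period's own baseline, in the 1, 2, 4 and 24 h, Follow-up or Pre-dose (Prior to Next Dose) block where it was recorded. The Final Visit block adds a second, misleading count. Listing 18 gives each interpretation with sequence, treatment, period and time point.
- **Few cases are likely.** The SAP cites a half-life of about 6 h and a washout of 8 days or more, and expects no carryover. Under protocol 7.3, abnormal assessments at check-in for Periods 2 to 4 are reviewed before dosing and recorded as AEs, which SAP 9 assigns to the treatment preceding their start. Eligibility is re-confirmed before each dose, and a clinically significant abnormal ECG is an exclusion. Persistent NCS findings are the realistic exposure.
- **No directional bias is shown.** A reader might infer that the distortion is worst between zoliflodacin and placebo. The documents do not support that: completers in every column have had all four treatments, the moxifloxacin column has the same structure as the placebo column, and SAP 9.8 plans no test or contrast for this table.
- **Two categories for one ECG is intended.** SAP 3.3 deliberately uses two baselines at the Final Visit, so the two blocks can differ. That is not a defect in itself, and the difference would remain in the Any Period column after any fix.

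The column assignment is also inferred from SAP 3.3, 9 and 9.8; it is not written in Table 27. The inference is direct, however, and the shell offers no other rule. These points limit the consequence but do not justify treatment columns for a whole-study shift.

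**Conclusion.** The point holds, with narrow reach. As laid out, the four treatment columns of the Final Visit block report a whole-study change under the Period 4 drug, against the purpose that SAP 3.3 gives for that baseline and unlike every other shell with this time point. The per-treatment counts are uninformative about the named drug, and an abnormality from Periods 1 to 3 that persists to the Final Visit would appear there as a fresh shift under the last drug, including placebo.

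The columns hold 18 of 72 subjects each if all complete. That is a column size and not a count of errors. Adding the placebo and moxifloxacin columns (18 + 18 = 36 of 72) might tempt a reader to call half the entries wrong. That total includes everyone who was normal at both times, and it assumes no dropout. Only persistent abnormalities that began before Period 4 are misread; their number cannot be derived from the documents.

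The Follow-up block, the Any Period column, the earlier time-point blocks and the Holter QTcF analysis are not affected. The conclusion assumes that the programmer applies the SAP 3.3 attribution rule to this block as SAP 9 directs.

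**What to change.** In Table 27, fill the Final Visit block (baseline before dose 1) under Any Period only and leave the four treatment columns blank, following Tables 20, 25 and 28. Add a short implementation note saying so. Leave the by-treatment reading of the same ECG to the Follow-up block, with the reading before dose 4 as baseline.

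The cost is one edit to a table shell before programming. No valid information is lost, because the Follow-up block already gives the by-treatment shift and the Any Period column keeps the overall one.

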14.4 Summary of Prior and Concomitant Medications

Table 30: Number and Percentage of Subjects with Prior Medications by WHO Drug Classification and Sequence

[Instruction: Include prior medications (medications with an end date prior to first dose) only.]

WHO Drug Code Level 1, Anatomic Group	WHO Drug Code Level 2, Therapeutic Subgroup	ABCD (N=X)	ACDB (N=X)	ADBC (N=X)	BADC (N=X)	BDCA (N=X)	BCAD (N=X)	CDAB (N=X)	CABD (N=X)	CBDA (N=X)	DCBA (N=X)	DBAC (N=X)	DACB (N=X)	All Subjects (N=X)
		n (%)												
Any Level 1 Codes	Any Level 2 Codes	x (x)												
[ATC Level 1 - 1]	Any [ATC 1 - 1]	x (x)												
	[ATC 2 - 1]	x (x)												
	[ATC 2 - 2]	x (x)												
	[ATC 2 - 3]	x (x)												
[ATC Level 1 - 2]	[ATC 2 - 1]	x (x)												
	[ATC 2 - 2]	x (x)												
	[ATC 2 - 3]	x (x)												

Treatment A = 2 g zoliflodacin; Treatment B = 4 g zoliflodacin; Treatment C = placebo; Treatment D = 400 mg moxifloxacin

Table 31: Number and Percentage of Subjects with Concomitant Medications by WHO Drug Classification and Treatment

[Instruction: Include concomitant medications (medications that are ongoing or that have an end date after first dose) only. The associated treatment for a concomitant medication should be the last treatment received prior to the start of the medication.]

WHO Drug Code Level 1, Anatomic Group	WHO Drug Code Level 2, Therapeutic Subgroup	2 g Zoliflodacin (N=X)	4 g Zoliflodacin (N=X)	Placebo (N=X)	400 mg Moxifloxacin (N=X)	Any Treatment (N=X)
		n (%)	n (%)	n (%)	n (%)	n (%)
Any Level 1 Codes	Any Level 2 Codes	x (x)	x (x)	x (x)	x (x)	x (x)
[ATC Level 1 - 1]	Any [ATC 1 - 1]	x (x)	x (x)	x (x)	x (x)	x (x)
	[ATC 2 - 1]	x (x)	x (x)	x (x)	x (x)	x (x)
	[ATC 2 - 2]	x (x)	x (x)	x (x)	x (x)	x (x)
	[ATC 2 - 3]	x (x)	x (x)	x (x)	x (x)	x (x)
[ATC Level 1 - 2]	[ATC 2 - 1]	x (x)	x (x)	x (x)	x (x)	x (x)
	[ATC 2 - 2]	x (x)	x (x)	x (x)	x (x)	x (x)
	[ATC 2 - 3]	x (x)	x (x)	x (x)	x (x)	x (x)

